### **Introduction**

Growing evidence in literature is supporting the role of ultrasound scan (US) as accurate tool in diagnosis and staging of gynecologic cancers [1]. In particular, different studies demonstrated the accuracy of US in assessing endometrial [2], cervical [3], and ovarian cancer [4] in the primary setting. However, the number of studies investigating the role of US in the recurrent setting is limited [5-7]. Moreover, there is no evidence in literature exploring the role of US in laterally-extended pelvic recurrences from gynecologic cancer [8], where the Magnetic Resonance Imaging (MRI) scan is still considered the most accurate tool [9].

### **Objective of the study**

The objective of the study is to assess the performance of US in patients undergoing pelvic exenteration and laterally extended pelvic resection.

The primary objective of the present study is to evaluate the accuracy of US in the assessment of pelvic structures involvement in recurrent/persistent gynecologic tumors with disease limited to the pelvis.

Secondary objective is to compare accuracy of US with the accuracy of MRI scan using histology as standard.

### **Type of study**

Prospective, observational, cohort, single center

### **Inclusion criteria**

All consecutive patients with histologically-proven recurrent or persistent gynecological cancer who are planned to undergo pelvic exenteration or laterally extended pelvic resection, both with curative and with palliative intent.

- Anterior/total pelvic exenteration
- Laterally extended endopelvic resection (LEER) [10]
- Laterally extended pelvic resection (LEPR) is defined as an en bloc lateral resection of a pelvic tumor involving sidewall muscle, and/or bone, and/or major nerve, and/or major vascular structure [8]
- With or without stoma formation

### **Exclusion criteria**

- Radical hysterectomy without lateral resection
- Rectal resection only (posterior exenteration)

### **Methods**

All consecutive patients who are planned to undergo pelvic exenteration or laterally extended pelvic resection at Policlinico Agostino Gemelli IRCCS, will undergo ultrasound scan at the time of the pre-operative anesthetic assessment or the day before the planned surgery. A pre-defined case report form (CRF) will be filled by the ultrasound examiner (Supplement 1). The ultrasound characteristics will be compared with the final histology (considered the referral standard).

The ultrasound examinations will be carried out using high-end ultrasound equipment. The frequency of the vaginal probes varied between 5.0 and 9.0 MHz. All examinations will be performed by a specialist obstetrics and gynecology with expertise in gynecologic oncology ultrasound scan. A subjective semi-quantitative assessment of the amount of blood flow within the examined lesion will be made (color score): a score of 1 was recorded when no blood flow could be found; 2 when only minimal/moderate flow could be detected; 3 when very strong blood-flow signals were present.

All patients will undergo pre-operative MRI scan and PET/CT scan.

Pelvic exenteration and laterally-extended pelvic resection will be performed with the aim to remove en bloc the recurrent or persistent disease with a free-of-tumor margin.

### *Statistical analysis*

The sample will be described in its clinical and demographic features using descriptive statistics techniques. Quantitative variables will be described using the following measures: minimum, maximum, range, mean and standard deviation. Qualitative variables will be summarized with absolute and percentage frequency tables. Normality of continuous variables will be checked using Kolmogorov-Smirnov test.

Cohen's Kappa Statistical test will be used to assess concordance between US and histology. Statistical analyses will be performed using the Statistical Package for Social Sciences software (PASW version 26.0, SPSS Statistic, IBM corp., New York, NY, USA). Two-sided tests will be used and the significance level was set at  $p < 0.05$ .

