#### *Sample size*

Given the primary objective and the assuming a degree of disagreement of 15%, setting  $\alpha=0.01$  and power=80%, the required sample size is N=85 [11].

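### The primary objective is the accuracy of ultrasound against histology, but the only method the protocol names is Cohen's kappa, which does not estimate accuracy

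*Protocol*

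**What the plan says.** - **Primary objective** (Protocol, Objective of the study): to "evaluate the accuracy of US in the assessment of pelvic structures involvement" in recurrent or persistent gynecologic tumors confined to the pelvis.
- **Secondary objective** (same section): to "compare accuracy of US with the accuracy of MRI scan using histology as standard".
- **Reference** (Protocol, Methods): "The ultrasound characteristics will be compared with the final histology (considered the referral standard").
- **Analysis** (Protocol, Statistical analysis): "Cohen's Kappa Statistical test will be used to assess concordance between US and histology". The rest of the section covers descriptive summaries, a normality check, software and the significance level. Sensitivity, specificity, predictive values and overall accuracy are named nowhere in the protocol.
- **Planning value** (Protocol, Sample size): "Given the primary objective and the assuming a degree of disagreement of 15" per cent, with alpha 0.01 and 80% power, leading to N=85. The disagreement is a single figure, not divided into missed involvement and false-positive involvement.

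**The concern.** A study of accuracy against a reference standard is asymmetric: histology is taken as the truth and US is judged against it. Kappa treats the two as interchangeable raters. This has two consequences.

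1. A miss and a false alarm both count simply as disagreement. If kappa is the headline result, a reader cannot tell a US examination that overlooks involved structures from one that reports involvement that is not there.
2. The chance correction depends on how often the structure is involved. Structures with different involvement rates would show different kappas even if US performed equally well on all of them.

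The single disagreement figure behind the sample size pools the same two errors, so the planning does not separate them either.

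**Working it through.** **The plan's own figure.** N=85 does not follow from the stated inputs, because no null value, margin or interval half-width is given. It can be reached only with an added assumption. For example, a two-sided 99% interval of half-width 10 points around 15% needs 2.576² × 0.15 × 0.85 / 0.10² = 84.6, so 85, but then the stated power plays no part. Nothing below depends on how N was obtained; 85 is used as given.

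**Inputs.** From the protocol: N=85 and about 15% disagreement. Assumed for illustration: one binary call per patient and structure (involved or not; the case report form is not shown), and the prevalences and counts below.

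**Formula.** Kappa = (Po − Pe)/(1 − Pe), where Po is observed agreement and Pe is the agreement expected from the margins. With prevalence p, sensitivity Se and specificity Sp, the US-positive rate is q = p·Se + (1 − p)(1 − Sp), and Pe = p·q + (1 − p)(1 − q).

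**Check 1: same accuracy, different kappa.** With Se = Sp = 0.85, Po = 0.85 at every prevalence.

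| Prevalence | q | Pe | Kappa |
|---|---|---|---|
| 50% | 0.500 | 0.500 | 0.70 |
| 30% | 0.360 | 0.556 | 0.66 |
| 20% | 0.290 | 0.626 | 0.60 |
| 10% | 0.220 | 0.724 | 0.46 |
| 5% | 0.185 | 0.7835 | 0.31 |

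For example, at 10%: (0.85 − 0.724)/(1 − 0.724) = 0.126/0.276 = 0.46.

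**Check 2: same kappa, different accuracy.** 85 patients, 42 involved and 43 not, 13 discordant (13/85 = 15.3%), so Po = 72/85 = 0.847 throughout. Kappa intervals use the large-sample (non-null) standard error; sensitivity and specificity intervals are Clopper-Pearson.

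| Misses / false alarms | Kappa (95% CI) | Sensitivity (95% CI) | Specificity (95% CI) |
|---|---|---|---|
| 13 / 0 | 0.69 (0.55 to 0.84) | 29/42 = 69% (53% to 82%) | 43/43 = 100% (92% to 100%) |
| 6 / 7 | 0.69 (0.54 to 0.85) | 36/42 = 86% (71% to 95%) | 36/43 = 84% (69% to 93%) |
| 0 / 13 | 0.70 (0.55 to 0.84) | 42/42 = 100% (92% to 100%) | 30/43 = 70% (54% to 83%) |

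The kappa intervals nearly coincide. The sensitivity intervals in the first and last rows do not overlap, nor do the specificity intervals.

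**Check 3: away from 50% prevalence.** With 17 of 85 involved and again 13 discordant, all misses (4 detected, no false alarms) gives kappa 0.33 and sensitivity 4/17 = 24% (7% to 50%). All false alarms (17 detected, 13 false positives) gives kappa 0.63 and sensitivity 17/17 = 100%. Here kappa does respond to the type of error, but a single value still cannot be split back into the two.

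The first of these tables would also count as significant if kappa were tested against zero: null standard error 0.0805, z = 0.330/0.0805 = 4.1, asymptotic p<0.001 (Fisher exact p = 0.0012). The protocol does not state the null, so this is conditional.

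**The case against.** **It belongs in the analysis plan.** The plan is not shown, the protocol does not call kappa the primary or sole analysis, and accuracy measures could be added without contradiction. It is true that the protocol does not label kappa as primary. But it is not silent either: kappa is the one method it commits to for US against histology, and that method does not match its own objective.

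**Accuracy may mean the proportion correct.** The term is undefined, and on this reading 15% disagreement is simply one minus accuracy, a coherent planning value. That defends the planning figure to some extent. It does not rescue kappa, which in check 1 runs from 0.70 to 0.31 while the proportion correct stays at 85%.

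**Nothing is lost.** Sensitivity and specificity come from the same cross-table. This is correct, and it limits the harm to pre-specification and reporting. The protocol does not, however, promise to report that table.

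**The examples are favorable choices.** Partly so. The near-identical kappas in check 2 arise because prevalence is close to 50%; check 3 shows a spread of 0.33 to 0.63 at 20%. And a kappa of 0.33 (95% CI 0.08 to 0.58) would itself signal weak agreement, so only its p-value misleads. These points qualify the illustrations, not the mismatch.

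**Conclusion.** The concern holds. The protocol asks how accurate US is against a reference standard and names an agreement index that estimates neither the sensitivity and specificity pair nor the proportion correct. How large the distortion will be in this study cannot be known, since involvement rates are not given and a binary call per patient and structure is assumed. That kappa depends on prevalence and cannot be split into its two error types is algebraic and needs no particular prevalence. The point should be fixed. It affects the primary objective, but the data to be collected already support the right analysis.

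**What to change.** **Statistical analysis section.** Make the sensitivity and specificity of US against histology, with exact 95% confidence intervals, the primary analysis for each structure that has histology. Report how many patients have histology for each structure. Give predictive values, overall accuracy and kappa, with intervals, as supportive.

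**Sample size section.** State the precision that N=85 gives for sensitivity and specificity. With both near 85%, and assuming that all 85 patients have histology for the structure:

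| Involved / not involved | Sensitivity, 95% CI | Specificity, 95% CI |
|---|---|---|
| 42 / 43 | 36/42: 71% to 95% | 36/43: 69% to 93% |
| 26 / 59 | 22/26: 65% to 96% | 50/59: 73% to 93% |
| 17 / 68 | 14/17: 57% to 96% | 58/68: 75% to 93% |
| 9 / 76 | 8/9: 52% to 99.7% | 65/76: 76% to 93% |

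**Cost.** Rewording and a precision statement; no extra patients or data. The downside is visible in the table: sensitivity is poorly estimated for rarely involved structures, and incomplete histology widens every interval. Two limits remain. Several structures give several primary estimates, so any single headline structure should be named in advance. And if imaging influences what is resected, restricting the analysis to structures with histology can bias the estimates, which the number verified per structure helps a reader to judge. A precision statement also does not say which test the stated alpha and power belong to; that needs separate attention.

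### The only inference named for US accuracy is a kappa test at p<0.05, which by default tests chance agreement; at N=85 a kappa of about 0.21 passes, so significance says little about accuracy

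*Protocol*

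**What the plan says.** The Objective section of the protocol sets the primary aim: to "evaluate the accuracy of US in the assessment of pelvic structures involvement" in recurrent or persistent gynaecological tumours confined to the pelvis. Under Methods, histology is the reference: "The ultrasound characteristics will be compared with the final histology (considered the referral standard").

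The Statistical analysis section names a single analysis of US against histology: Cohen's "Kappa Statistical test will be used to assess concordance between US and histology". After a sentence on software it adds "Two-sided tests will be used and the significance level was set at" p<0.05. It states no null kappa, minimum acceptable kappa, confidence interval, sensitivity or specificity.

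The Sample size section works from a different quantity, "assuming a degree of disagreement of 15" per cent, with α=0.01 and 80% power, and concludes that "the required sample size is N=85". It names no test and no null or comparison value.

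**The concern.** The objective asks how accurate US is. A kappa test with no stated null asks whether US and histology agree more often than chance would produce. These are different questions. A small p-value on the second does not show that US finds involved structures often enough to be useful.

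The test is also unconnected to the planning value. The study is sized around 15% disagreement, but nothing in the test refers to 15%. Depending on how common involvement is, the test can be significant at disagreement well above 15%, or fail to be significant at 15% itself. A reader given only the kappa p-value could not tell good US from poor US.

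**Working it through.** **Inputs.** From the protocol: N=85, two-sided p<0.05, planned disagreement 15%. Assumed, because the protocol does not give them: one yes/no call per patient, equal proportions positive on US and histology, and an involvement prevalence π varied from 10% to 50%.

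**The plan's own figure.** N=85 cannot be derived from 15% disagreement, α=0.01 and 80% power alone, because a null or comparison value is missing. A kappa test against zero does not give it either. With n = ((z_α + z_β)/κ)² and two-sided α=0.01, 15% disagreement needs ((2.576+0.842)/0.70)² ≈ 24 patients at 50% involvement and ((2.576+0.842)/0.531)² ≈ 42 at 20%. N=85 is taken as given below.

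**Step 1, the smallest significant kappa.** Under kappa = 0,

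SE₀ = √(Pe + Pe² − Σ pᵢqᵢ(pᵢ+qᵢ)) / ((1−Pe)√n),

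where Pe is chance agreement and pᵢ, qᵢ are the two sets of margins. For a 2×2 table with equal margins this reduces to 1/√n = 1/√85 = 0.1085, whatever the prevalence. The threshold is 1.96 × 0.1085 = 0.213.

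**Step 2, what that threshold means.** With equal margins, Pe = π² + (1−π)², disagreement d = (1−κ)(1−Pe), and misses equal false alarms at d/2. Sensitivity is then 1 − d/(2π).

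| Involvement π | 1−Pe | Disagreement at κ=0.213 | Sensitivity |
|---|---|---|---|
| 50% | 0.500 | 39.4% | 61% |
| 30% | 0.420 | 33.1% | 45% |
| 20% | 0.320 | 25.2% | 37% |
| 15% | 0.255 | 20.1% | 33% |
| 10% | 0.180 | 14.2% | 29% |

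As involvement becomes rarer, the tolerated disagreement falls, but so does the sensitivity at the threshold.

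**Step 3, the planned 15%.** At 50% involvement κ = 1 − 0.15/0.50 = 0.70. At 20% it is 1 − 0.15/0.32 = 0.53. At 10% it is 1 − 0.15/0.18 = 0.17, and z = 0.167/0.1085 = 1.54, which is not significant.

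**Step 4, how often poor US would reach p<0.05.** By simulation at 50% involvement the probability is 97% at a true disagreement of 30%, 80% at 35% and 45% at 40%. At 30% involvement it is 96% at 25% disagreement and 74% at 30%. At 20% involvement it is about 52% at 25% disagreement.

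**Step 5, sensitivity to assumptions.** At α=0.01 the threshold is κ=0.279, with disagreement of 36.0% at 50% involvement and 23.1% at 20%. Unequal margins can push the figure higher: with 30% against 60% positive, the largest significant disagreement is 44.5%.

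**The case against.** The strongest reply is that the protocol sets no decision rule. It says that kappa will be used to assess concordance. The sentence on two-sided tests and p<0.05 comes later and covers all tests. The study is observational, and the authors may intend to interpret the size of kappa. This stands in part. A reader might infer that a significant kappa is the declared success criterion, but no section says so. What remains is that a test at p<0.05 is the only inference supplied for the primary objective.

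A second reply is that intervals and nulls are commonly left to an analysis plan, which is not shown here. That is fair for absent detail. But the protocol does fix the test and its level for the primary objective, and the fixed method is a poor match to an accuracy question.

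A third reply concerns size. A reader might infer that 25–39% of patients could be misclassified with significance in general. The documents do not support that: the range needs 20–50% involvement, equal margins and one call per patient, whereas the objective speaks of structures in the plural. At 15% and 10% involvement the figure drops to 20% and 14%. Nor do the documents show that beating chance is a foregone conclusion. The Introduction says evidence on US in laterally extended recurrence is lacking.

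**Conclusion.** The point holds in limited form. The one inference the protocol names for US against histology is, by the usual convention, a test of kappa = 0. It cannot answer the accuracy objective and is unrelated to the 15% disagreement behind the sample size. At N=85 with equal margins, significance starts at a kappa of about 0.21. With one call per patient, sensitivity at that threshold is no higher than 61% at any tabulated involvement from 10% to 50%. The kappa threshold needs only N, the 5% level and equal margins. The disagreement and sensitivity figures also depend on prevalence and unit of analysis, which the protocol leaves open. The conflict between α=0.01 and p<0.05 is a separate matter, and using 0.01 does not change the conclusion.

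**What to change.** In the Statistical analysis section, replace the p-value against zero as the primary inference with two results:

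- kappa with its 95% confidence interval;
- sensitivity and specificity of US against histology, each with an exact 95% interval.

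If a verdict of adequacy is wanted, require the lower 95% limit of kappa, or of sensitivity and specificity, to exceed a minimum that the sponsor states in advance. Do not base it on raw disagreement alone. At about 15% involvement, a reader who calls every patient uninvolved would disagree in 13/85 (exact 95% interval 8.4% to 24.7%), which looks acceptable, yet has sensitivity 0 and kappa 0.

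For orientation, at 15% disagreement with N=85, equal margins and the large-sample standard error, kappa is 0.70 (95% CI 0.55 to 0.85) at 50% involvement and 0.53 (0.31 to 0.76) at 20%.

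The cost is a sentence or two and no new data. The downside is that a favourable claim becomes harder to make than with p<0.05 against chance.

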#### *Sample size*

Given the primary objective and the assuming a degree of disagreement of 15%, setting  $\alpha=0.01$  and power=80%, the required sample size is N=85 [11].

